The Actiheart device is supplied by the CNRC team to the research team. The device will be provided to and collected from the participant via FedEx service or will be handed to the patient at one of the research visits (example: screening visit). After the completion of data collection by the participant, the research team will physically hand the device to the CNRC team for further data analysis. Each device will have a patient number that was coded by the research team. CNRC team will have no participant's identifying data on the device. CNRC team will receive subject's gender, height, weight, and date of birth to help in data analysis. For data analysis, CNRC staff has controlled access to the Actiheart device database which is maintained on BCM IT server. Also, the data collected is not shared with device manufacturer or any other third party.

Please note: The CNRC staff has provided the Actiheart device information and will provide statistical analysis for the study.

Where applicable, all research data will be coded and transmitted via secure e-mail accordingly.

Will you obtain a Certificate of Confidentiality (COC) for this study?

No

Please further discuss any potential confidentiality issues related to this study.

N/A

Section L: Cost/Payment

Delineate clinical procedures from research procedures. Will subject's insurance (or subject) be responsible for research related costs? If so state for which items subject's insurance (or subject) will be responsible (surgery, device, drugs, etc). If appropriate, discuss the availability of financial counseling.

Research-related procedures are incurred by the study. There are no standard of care procedures for this study. Oxytocin will be covered by the study.

If subjects will be paid (money, gift certificates, coupons, etc.) to participate in this research project, please note the total dollar amount (or dollar value amount) and distribution plan (one payment, pro-rated payment, paid upon completion, etc) of the payment.

Dollar Amount:

400

Distribution Plan:

Each completed treatment period will involve \$200 in compensation for a total at \$400 for study participation. Additionally, reimbursement for applicable travel-related expenses (parking, mileage, ground transport, hotel and flights) will be covered ranging up to but not limited to \$600 for study participation. Study compensation and reimbursement will be provided through Baylor's ClinCard program.

Section M: Genetics

How would you classify your genetic study?

Discuss the potential for psychological, social, and/or physical harm subsequent to participation in this research. Please discuss, considering the following areas: risks to privacy, confidentiality, insurability, employability, immigration status, paternity status, educational opportunities, or social stigma.

n/a

Will subjects be offered any type of genetic education or counseling, and if so, who will provide the education or counseling and under what conditions will it be provided? If there is the possibility that a family's pedigree will be presented or published, please describe how you will protect family member's confidentiality?

n/a

Section N: Sample Collection

SAMPLE: Blood

What is the purpose of the sample collection?

Blood will be collected for the measurement of oxytocin levels. Blood will be also collected for storage for later confirmation of research findings.

For blood draws, specify the amount drawn, in teaspoons, at each visit and across the course of the subjects entire participation time.

All participants are adults. Blood will be collected on day 1 only. The two treatment periods are at least one month apart. On each treatment period, blood will be drawn prior to treatment and immediately after treatment.

Visit 1 in treatment period 1 - blood draw will include in each visit: Day 1 - Pre-treatment: 10 ml (2 teaspoons) for oxytocin measurements, 20 ml (4 teaspoons) for storage. immediately after treatment: 10 ml (2 teaspoons) for oxytocin measurements, 20 ml (4 teaspoons) for storage. Total of 60 ml of blood for this day (12 teaspoons).

Total blood collection during treatment period 1 - 60 ml (12 teaspoons)

Visit 1 in treatment period 2 - blood draw will include in each visit: Day 1 - Pre-treatment: 10 ml (2 teaspoons) for oxytocin measurements, 20 ml (4 teaspoons) for storage. immediately after treatment: 10 ml (2 teaspoons) for oxytocin measurements, 20 ml (4 teaspoons) for storage. Total of 60 ml of blood for this day (12 teaspoons).

Total blood collection during treatment period 1 - 60 ml (12 teaspoons)

Samples for oxytocin measurements will be obtained on ice and plasma will be stored immediately.

Is there the possibility that cell lines will be developed with this sample?No

Sample will be obtained from:

Other: Research subject

Will the sample be stripped of identifiers?

Νc

If sample will be released outside the hospital:

Will sample be released to anyone not listed as an investigator on the protocol? Will the information be identifiable, coded or de-identified?

Coded samples may be shared with other researchers. No access to PHI will be shared.

Will sample material be sold or transferred to any third parties? Will the information be de-identified?

No

If sample will be banked for future use:

Where will the sample be banked and for how long?

The blood samples drawn for storage will be processed and stored in locked freezers at the CNRC (Children's Nutrition Research Lab) lab. All frozen samples will be labeled with subject study number only.

Does the banking institution have an approved policy for the distribution of samples?

Yes

If the entire sample will NOT be used during the course of this research study:

Will the remaining tissue be discarded? If not what will be done with the remaining sample after study completion and how long will the sample be kept?

Any samples not used during the course of this study will be stored indefinitely and at the discretion of the Principal Investigator.

Will samples be made available to the research subject (or his/her medical doctor) for other testing?

No

If a subject withdraws from the study:

Will subject have the option to get the remaining portion of their sample back?

No

Will samples be destroyed? If not, will they be kept anonymously? What will happen to the sample if the subject revokes authorization?

If the subject revokes authorization prior to sample processing, all samples including the sample for storage will be destroyed.

Will data obtained from their sample be deleted? What will happen to the sample if the subject revokes authorization? If the subject revokes authorization, all data gathered from their samples, including storage samples, will be deleted.

Will study data or test results be recorded in the subject's medical records?

No

Will results of specific tests and/or results of the overall study be revealed to the research subject and or his/her doctor?

Results of cortisol levels can be revealed to the subject as the study is conducted. The results of Oxytocin levels will be revealed to the subject at study completion upon the subject's request. The subject may reveal these results to their doctor.

Please identify all third parties, including the subject's physician, to receive the test results.

No third parties will receive the test results.

SAMPLE: Urine

What is the purpose of the sample collection?

Urine sample will be collected for a urine pregnancy test to determine study eligibility.

For blood draws, specify the amount drawn, in teaspoons, at each visit and across the course of the subjects entire participation time.

N/A

Is there the possibility that cell lines will be developed with this sample? No

Sample will be obtained from:

Other: Research subject

Will the sample be stripped of identifiers?

No

If sample will be released outside the hospital:

Will sample be released to anyone not listed as an investigator on the protocol? Will the information be identifiable, coded or de-identified?

No.

Will sample material be sold or transferred to any third parties? Will the information be de-identified?

No.

If sample will be banked for future use:

Where will the sample be banked and for how long?

Nο

Does the banking institution have an approved policy for the distribution of samples?

No.

If the entire sample will NOT be used during the course of this research study:

Will the remaining tissue be discarded? If not what will be done with the remaining sample after study completion and how long will the sample be kept?

Yes, any remaining urine sample will be discarded once the urine pregnancy test has been administered.

Will samples be made available to the research subject (or his/her medical doctor) for other testing?

No

If a subject withdraws from the study:

Will subject have the option to get the remaining portion of their sample back?

No

Will samples be destroyed? If not, will they be kept anonymously? What will happen to the sample if the subject revokes authorization?

Yes, any remaining urine sample will be discarded once the urine pregnancy test has been administered.

Will data obtained from their sample be deleted? What will happen to the sample if the subject revokes authorization?

If data was collected prior to withdrawal, then that data will be kept. Any data collected after withdrawal will be deleted.

Will study data or test results be recorded in the subject's medical records?

Yes

Will results of specific tests and/or results of the overall study be revealed to the research subject and or his/her doctor?

Results from urine pregnancy test will be reported in hospital electronic medical record system, i.e., BCM EPIC or BSLMC EPIC.

Please identify all third parties, including the subject's physician, to receive the test results.

No third parties will receive test results.

Section O: Drug Studies

Does the research involve the use of ANY drug* or biologic? (*A drug is defined as any substance(other than food) that is used to elicit a pharmacologic or physiologic response whether it is for treatment or diagnostic purposes)

Yes

Does the research involve the use of ANY gene transfer agent for human gene transfer research? No

O1. Current Drugs

Drug 1: Oxytocin

If yes, be sure that you justify the use of the placebo for this research in the space below.

This is a single blind, fixed sequence, placebo-controlled study. Pain levels will be measured under the treatment with placebo in the first treatment period and will be compared to the measurements of the same parameters under the treatment with oxytocin in the second treatment period. This allows the comparison between the same individual subject's response to oxytocin compared to placebo.

Will the research involve a radioactive drug?

Nο

Section P: Device Studies

Does this research study involve the use of ANY device? Yes

Device 1: Actiheart

Section Q: Consent Form(s)

Evaluating the effect of IV (intravenous) Oxytocin on chronic pain in adult females with a clinical diagnosis of hypermobile Ehlers-Danlos syndrome (hEDS) that experience chronic pain

Section R: Advertisements

Mode of Advertising: Bulletin Board

Exact language of Advertisement:

ATTENTION: RESEARCH OPPORTUNITY

Baylor College of Medicine is conducting a research study looking at novel treatment option for chronic pain in adult females with hypermobile Ehlers Danlos Syndrome (hEDS)

Purpose of the study is to evaluate the effectiveness of novel treatment option for chronic pain in adult females with hypermobile Ehler Danlos Syndrome (hEDS).

Study involves two treatment periods that each includes a pre-treatment period of six days for chronic pain and anxiety evaluation followed by three days of daily infusions with blood draws along with orthopedic evaluations and ending with a post-treatment evaluation period of six days.

Study location will take place at Baylor College of Medicine McNair Campus and Baylor St. Luke's Medical Center (BSLMC).

Study compensation provided at \$200 per completed treatment period for a total of \$400 including parking and and other applicable travel-related expenses will be reimbursed.

For more information, please contact: [name] at [contact]

Mode of Advertising: Internet

Exact language of Advertisement:

We will recruit patients through the EDS society using the society website and social media platforms. The EDS society will be able to send a notification about this current study using a reference to the study as published in ClinicalTrials.gov or a flyer with details on this study, see attached in section S. Study staff will contact hEDS patients registered in the EDS society's registry who agreed to be contacted by research groups. This will be done through the DICE-EDS program (see https://www.ehlers-danlos.com/eds-global-registry/researcher-applications/).

Mode of Advertising: Other: BCM Social Media Platforms

Exact language of Advertisement:

We will recruit patients through Baylor College of Medicine social media platforms. Any social media account of Baylor College of Medicine, including but not limited to the Department of Molecular and Human Genetics, will be able to send a notification about this current study using a reference to the study as published on the BCM Clinical Trials Website.

Mode of Advertising: BCM Clinical Trials Website

Exact language of Advertisement:

ATTENTION: RESEARCH OPPORTUNITY

Baylor College of Medicine is conducting a research study looking at novel treatment option for chronic pain in adult females with hypermobile Ehlers Danlos Syndrome (hEDS)

Purpose of the study is to evaluate the effectiveness of novel treatment option for chronic pain in adult females with hypermobile Ehler Danlos Syndrome (hEDS).

Study involves two treatment periods that each includes a pre-treatment period of six days for chronic pain and anxiety evaluation followed by three days of daily infusions with blood draws along with orthopedic evaluations and ending with a post-treatment evaluation period of six days.

Study location will take place at Baylor College of Medicine McNair Campus and Baylor St. Luke's Medical Center (BSLMC).

Study compensation provided at \$200 per completed treatment period for a total of \$400 including parking and and other applicable travel-related expenses will be reimbursed.

For more information, please contact: [name] at [contact]

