Hypermobile EDS is more prevalent in females and the symptoms are usually more severe in females and more females come to medical attention. Oxytocin secretion in the body is dynamic and can be affected by multiple factors including the menstrual period. In order to have minimum variation between tested individuals we chose to conduct this study in females, all participants will be at the same stage of their menstrual cycles. We are not aware of any difference in the risk from using oxytocin in females vs males.

All participating individuals will be individuals affected with hypermobile-EDS (hEDS) with chronic moderate pain. Study will include two periods of treatment - one with placebo and one with oxytocin. Each period of treatment will include three consecutive daily infusions (placebo or oxytocin). Each participant will receive placebo infusion (normal saline) in the first treatment period and oxytocin infusion in the second treatment period. Each period will be preceded by 6 days of daily pain evaluation using pain-evaluation questionnaire ('pre-infusion evaluation'). This period (prior to placebo or prior to oxytocin treatment) will start 1-3 days after the end of the menstrual cycle. Participants will be blinded to the order of treatment.

For each treatment period, participants will arrive to the study site for three daily consecutive visits, each will last for 3-4 hours. Response variables will be collected prior, during and after each infusion. Patients will fill out pain evaluation questionnaires pre and post infusion. Blood pressure and heart rate measurements will be taken prior, during and after the infusion. Blood samples for measurements of oxytocin levels and blood samples for future analysis will be collected prior and after the infusion. Response to treatment by questionnaire will be evaluated also during 6 days after each three infusion days (placebo or oxytocin). Patients will be asked to wear the ACTIHEART device 3 days prior to infusion, during the 3 days of infusions, and in the 3 days after the last infusion.

Inclusion Criteria:

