1) Premenopausal Females, Age >18 years 2) Clinical diagnosis of hypermobile EDS according to the 2017 criteria for hEDS 3) Menstrual periods (range from 8 to 42 days) 4) Pain level greater that pain score of 4 out of 10 on a Numeric Rating Scale in at least two of the following locations: back, neck, shoulders, elbows, wrist, hand joints, hips, knees, ankles, on most days over the 3 months preceding enrollment. 5) On a stable regimen for pain control without any expected increase in dose of pain medications during the study period. 6) All participants should have a negative urine pregnancy test and agree to use an acceptable method of contraception (abstinence or barrier methods). 7) Current from the last year EKG report prior to the infusion for screening purposes. Otherwise, participant will need to have an EKG done in person at the screening visit on site.

Exclusion Criteria:

1) Known allergy to OXT or preservatives in the medication 2) Pregnancy 3) Lactation 4) A confirmed clinical diagnosis of autoimmune disorders that lead to joint inflammation and joint pain such as SLE, RA, psoriatic arthritis, ankylosing spondylitis, scleroderma, and enteropathic arthritis 5) History of known cardiac arrhythmias (except for asymptomatic sinus tachycardia and sinus bradycardia) 6) Heart rate persistently greater than 110/min or less than 50 per minute 7) QTC of > 450 ms from EKG (electrocardiogram) test 8) Taking oral or other hormonal contraceptives 9) Individuals with a clinical condition which, in the view of the investigator compromises safety 10) Participating in another interventional study.

F2. Procedure

This will be a single-blind, fixed-sequence study. This study will include two treatment periods. During the first period, placebo will be administered and during the second period, oxytocin will be administered. The participants will be blinded to the sequence of treatment assignment.

Each treatment period will start 7-12 days after the first day of menstruation and will be divided to the following: 1) preinfusion period of 6 days during which baseline pain and anxiety evaluation will be done, 2) infusion period that includes 3 consecutive days of infusions, 3) post-infusion evaluation period of 6 days during which post-treatment pain and anxiety will be evaluated.

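### Inclusion item 3 admits a menstrual range from 8 days, but a 15-day treatment block starting 7-12 days after menses begin cannot fit in a cycle of 8-21 days

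*Combined protocol and SAP*

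**What the plan says.** Section F1, Inclusion Criteria, item 3, sets the only limit on menstrual pattern: "Menstrual periods (range from 8 to 42 days". It does not say whether this is cycle length or duration of bleeding.

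Section F2 fixes the timing: "Each treatment period will start 7-12 days after the first day of menstruation and will be divided to the following" three parts. These are a "preinfusion period of 6 days during which baseline pain and anxiety evaluation will be done", an "infusion period that includes 3 consecutive days of infusions" and a "post-infusion evaluation period of 6 days during which post-treatment pain and anxiety will be evaluated". The second treatment period has the same 7-12 day anchor and must also begin at least two weeks after the first is completed.

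Section F1 gives the reason for timing by cycle: "Oxytocin secretion in the body is dynamic and can be affected by multiple factors including the menstrual period". To limit variation between individuals, it says that "all participants will be at the same stage of their menstrual cycles".

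The start is also described in two other ways. Section F1 places the pre-infusion evaluation 1-3 days after the end of what it calls the cycle. Section F2 places period 1 shortly after the menstrual period is over.

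**The concern.** An eligibility limit and a visit schedule should be compatible: a woman who meets the criteria should be able to follow the schedule at the cycle stage the design intends. Read as cycle length, a lower limit of 8 days does not allow that. Menses would return inside the baseline, infusion or post-infusion window, and the infusions could fall in a later cycle than the one used to time them.

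At stake is the variation that the design sets out to remove. The primary comparison in Section G2 is the pre-to-post change in pain under placebo against the same change under oxytocin. Menses in one of those windows could affect pain scores for reasons unrelated to the infusion. Section F2 does not say what to do if menses return during the block, and its eligibility screening list adds no check on cycle length.

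**Working it through.** The plan gives no minimum cycle length of its own to reproduce, so the check is calendar arithmetic on the Section F2 schedule.

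**Inputs.** Range 8 to 42 days (F1, item 3). Start s = 7 to 12 days after the first day of menstruation (F2). Segments of 6, 3 and 6 days (F2).

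**Convention and assumption.** The first day of menstruation is day 0. The range is taken as cycle length L, so the next menses begin on day L.

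**Formulas.**
- Block length: 6 + 3 + 6 = 15 days, covering days s to s + 14.
- The whole block precedes the next menses if L ≥ s + 15.
- Infusions fall on days s + 6 to s + 8, and all precede the next menses if L ≥ s + 9.
- Every infusion falls in a later cycle if L ≤ s + 6.

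| Start s | Block | Infusions | Minimum L, whole block | Minimum L, infusions only |
|---|---|---|---|---|
| 7 (earliest) | days 7-21 | days 13-15 | 22 | 16 |
| 12 (latest) | days 12-26 | days 18-20 | 27 | 21 |

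**Whole block.** Lengths 8-21 never fit, lengths 22-26 fit only with an early enough start, and lengths 27-42 always fit. That is 14, 5 and 16 of the 35 whole-day lengths allowed. If 7-12 is read as numbered cycle days with the first day as day 1, the minimum becomes 21 to 26.

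**Infusions only.** Lengths 8-15 fail at every permitted start. With s = 7, every infusion falls in a later cycle when L ≤ 7 + 6 = 13. Later starts give larger bounds, so for L ≤ 13 this holds at every permitted start.

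**At the stated lower limit, L = 8.** New menses begin on days 8, 16 and 24. Starts 8-12 days after the first day already lie in the next cycle. A start on day 7 has new menses on the second pre-infusion day (day 8) and the first post-infusion day (day 16).

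**Differing starts in the two periods.**
- L = 24: a start on day 7 is free of new menses. A start on day 12 has them on day 24, which is post-infusion day 4.
- L = 18: a start on day 7 puts them on post-infusion day 3, a scheduled pain-questionnaire day. A start on day 12 puts them on the first infusion day.

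**If the figure means days of bleeding.** Eight days of bleeding covers days 0-7, so a start on day 7 is not after its end. Thirteen days or more covers days 0-12, which is every permitted start. That conflicts with the F2 statement that period 1 follows the end of the menstrual period.

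**The case against.** Five points can be made on the other side.

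- No section says that all 15 days must precede the next menses. F2 anchors only the start, and F1 says only that the stage is the same. This stands: the 22 to 27 day minimum is an inference. On the weaker requirement that only the infusions come first, the minimum drops to 16 to 21 days, which a limit of 8 still does not meet.
- The wording refers to periods, not cycles, and the documents use the two terms loosely. This also stands, but it does not rescue item 3, because the bleeding reading conflicts with the start rules.
- The primary comparison is paired, and both periods have the same anchor. For a woman with a stable cycle and the same start day, menses fall at the same point in both blocks and much of the effect cancels. That is fair. The cancellation is incomplete because start days may differ by up to 12 − 7 = 5 days, as the 24-day and 18-day examples show.
- The 8 may be a typing error, and the enrollment checklist, whose content the protocol text does not give, may be stricter. Neither can be shown. As written, 8 is the eligibility limit.
- Section F1 also justifies a female-only study by prevalence and severity. That is correct: cycle control is one of the reasons given, not the only one.

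**Conclusion.** Wrong as written: item 3 and the F2 schedule cannot both be followed by every eligible woman at the intended cycle stage. On the cycle-length reading, lengths of 8-21 days fail for the whole block, and lengths of 8-15 days fail even if only the infusions must precede the next menses. The result rests on the cycle-length reading and, for the larger set, on the inferred one-cycle requirement. The bleeding reading leads to a different conflict.

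Three stronger conclusions might be inferred and are not supported:
- It does not follow that every cycle under 27 days is unworkable. Lengths of 22-26 days can hold the block with an early enough start.
- The 14 of 35 lengths is a count of integers, not a proportion of women. The documents give no cycle-length distribution, so the number affected cannot be derived.
- Bias in the oxytocin-placebo contrast is not shown. The documents give no reason for start days to differ systematically between periods. What can be said is that avoidable variation is admitted, with partial cancellation through pairing.

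**What to change.** State in item 3 whether the figure is cycle length, days of bleeding or something else. Then reconcile item 3 with the F2 schedule and with the start descriptions: 7-12 days after the first day for both periods (F2), 1-3 days after the end of the cycle (F1), and shortly after the end of the menstrual period for period 1 (F2). The result should be that every eligible woman can follow the schedule at the intended stage. State also whether the whole block or only the infusions must precede the next menses. The sponsor decides whether the eligibility range or the schedule changes; no value is proposed here.

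The cost is small. If only the range changes, it is a one-line amendment, and a few women with short cycles may no longer qualify. If the schedule changes, the advertisement text in Section R, which repeats the six, three and six days, would need the same edit.
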